3. TRIAL DESIGN

The design of the proposed main trial work has been developed with reference to CONSORT (http://www.equator-network.org/reporting-guidelines/consort/) and SPIRIT guidelines (http://www.spirit-statement.org/), and the TIDieR checklist and guide (http://www.bmj.com/content/348/bmj.g1687).

MAIN TRIAL

Our trial will be a multicentre rater-blinded (primary outcome) RCT with 2 parallel arms. It will compare a psychological intervention (CBT_{BAR}) + TAU (treatment condition) to TAU alone (control condition). The trial will recruit 338 participants who meet the Bipolar At Risk (BAR) criteria and randomly allocate them to a 6-month package of either condition.

Randomisation will be independent and concealed, using permuted stratified blocks, where site (5-levels) and BAR group (3-levels) are the stratification factors. It will be conducted via a web-based system conducted within York CTU. Assessors will be masked to allocated treatment. Masking will be maintained using a wide range of strategies (e.g. separate offices for therapists and researchers, protocols for answering phones, message taking and secretarial support, separate diaries and security for electronic randomisation information).

Assessor's blind and independent to treatment group will collect all outcome and mediational variables at baseline, 17-weeks (during treatment window capturing SCID-5 + PSR's (SCID LIFE), HAPPI, BC and ISS), 27-weeks (after therapy cessation), and at 52-weeks. Participants will receive £20 reimbursement upon completion at each assessment point as a thank you for their time.

The assessors will also contact people via phone at 39-weeks to promote retention in the trial. We will ask about general wellbeing since the last assessment (including documenting any potential serious adverse events), and any changes to contact details. Participants will receive a £5 supermarket voucher of their choice to thank them for their continued participation.

For those participants who are randomly selected to receive the CBT_{BAR}, they will be offered up to 26 individual weekly therapy sessions of up to 60 mins in length. These will be delivered by a Clinical Psychologist or psychological therapist.

NESTED QUALITATIVE WORK

In addition to the main trial, we will also be conducting qualitative interviews/focus groups to understand the perceived mechanisms of change for the participants offered the CBT_{BAR} (mechanistic objective), as well as the implementation of CBT_{BAR} in NHS services (implementation objective).

We will recruit two groups of up to 25 participants. The first group will be participants from the treatment arm across of 5 sites. The 2nd group will be key stakeholders including health professionals, service providers, commissioners, service providers/leads, clinicians, and service users.

Sampling will be purposive. For the implementation group we will be recruiting participants who received the CBT_{BAR}, their family members, and a mix of health professionals including those delivering the therapy, those who are experienced in delivering CBT, and commissioners. For the perceived mechanism of change group we will be recruiting participants who scored differently on the therapeutic alliance measure, who have varying mood experiences following the intervention (as measured by the SCID-5 + PSR's (SCID LIFE)), and who have varying change in their appraisals (as measured by the HAPPI). For both the implementation and perceived mechanism of change interviews with our service user participants, we will seek a diverse & inclusive sample (e.g. ethnicity, socioeconomic status, gender), level of engagement in therapy, and non-responders. We will be considering what services the BAR group of young people are currently accessing e.g. primary care and take into account the different service set ups across the multiple sites taking part in this trial.

Participants who take part in a qualitative interview/focus group will receive £20 reimbursement for their time.

Sample Size

Sample size: quantitative work

Whilst we plan to include LIFE depression and LIFE mania 4-week average PSR scores as co-primary outcomes, overall symptom severity of depression is greater compared with mania in this population, as is its standard deviation [80]. Although it may be argued that a minimally clinically important difference (MCID) in LIFE PSR mania score is somewhat smaller than the MCID for the PSR depression score, the relative difference will be smaller than that for the SD. This means that the Standardised Effect Size (SES) will be smaller for depression than that for mania and, therefore, that the sample size to detect the MCID will be greater for depressed mood

than for mania. On the LIFE PSR, our eligible population will score at the higher end of the subthreshold range (3-4) as those scoring 5-6 will confer research diagnostic criteria and therefore not meet the inclusion criteria for the trial; based on our pilot trial (mean baseline BDI-II score of 37.9), participants will tend to be towards the upper end of the subthreshold range (i.e. mean around 3.75). Button [81] reported that a MCID for the BDI-II is around 17-18%; given that we expected similar sensitivity for the mean LIFE depression PSR scores as would be the case for BDI-II, a difference of around 0.5 points (0.18*[3.75-1]=0.50 (to 2 d.p.)] on the PSR for LIFE depression in order to indicate that CBT_{BAR} is having an important effect.

To detect a between-group mean difference of 0.5 points (SD=1.3 points [80]) on the mean 4-week PSR for LIFE depression score at 27-weeks follow-up we require 286 participants with outcome data to achieve 90% power, using an ANCOVA (with 2.5% two-sided significance level), assuming a conservative correlation of 0.4 between baseline and 27-week scores [82]. Inflating the sample size to allow for a conservative 15% attrition (attrition was 13% in our feasibility trial, 57) requires a target to randomise of 338 participants (approx. 68 per site). This sample size will provide greater than 90% power to detect a rather more conservative MID on LIFE PSR for mania (e.g. equating to 98.5% to detect a target effect of 0.25 points [estimated within-group SD=0.5 points]) [80]. In each case, power will be increased due to the (multiple) correlation between outcome and the full set of explanatory variables adjusted for in the model. We have not allowed for a random therapist effect in our sample size calculation as the effect on depression outcome (BDI-II) in our pilot trial was 0, although the confidence interval was wide; we will, however, include the addition of a random therapist effect amongst our sensitivity analyses.

Assuming a standardised effect size of the intervention on the HAPPI of 0.4, 286 participants with mediator and primary outcome data will also allow for 88.5% power for estimation of an indirect effect of 40% via the putative primary mediator (HAPPI), or 83.5% power for the estimation of a 30% indirect effect, based on a total effect on the intervention of the MCID (i.e. 0.5) (with a 2.5% significance level, estimated using the R package medssp, based functions provided in Vittinghoff and Neilands [83]

Sample size: qualitative work

We will recruit two groups of 15-25 people each for individual interviews as part of the qualitative work: 1 group will be participants from the treatment arm of the trial across all 5 sites and 1 group will be comprised of key stakeholders including health professionals and service providers and commissioners. Sampling will be purposive, seeking to ensure maximum variance in the final sample and, seeking disconfirming cases where relevant. For the service user group we will ensure participants are drawn from across all 5 trial sites, and in order to build upon the acceptability work in the original BART trial will seek a more diverse and inclusive sample (e.g. ethnicity, socioeconomic status, gender) and level of engagement in therapy, including non-responders. The stakeholder groups will include health professionals involved in delivery of CBT_{BAR} and other interventions and services for this population, and referrers (and potential referrers) to the trial from a range of services and across geographical area.

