8. STATISTICS & DATA ANALYSIS

MAIN TRIAL DATA ANALYSIS

All comparative analyses will be 'as randomised', where participants are analysed according to the group they were randomised to, regardless of what treatment they received. Complete details of analyses will be included in a Statistical Analysis Plan which will be finalised and approved by the Trial Steering Committee prior to database lock and prior to any analysis.

Co-primary outcomes

The primary analyses for each of the co-primary outcomes (mean 4-week PSR for LIFE depression score and for LIFE mania score at 27-week follow-up) will use ANCOVA, with adjustment for the stratification factors (site and BAR group) and the baseline PSRs for depression and mania and prior CBT (yes/no). Missing data will be explored; for each co-primary, if less than 15% are missing, and less than 10% differential missing data, then case analysis (CCA) will be used, otherwise it will be multiple imputation by chained equations (MICE) [94] assuming that the data are 'missing at random'. Tests will use a 2.5% significance level and two-sided 97.5% confidence intervals (CIs) will be presented.

Moderator: We will explore BAR group (I, II or II) and prior CBT (yes; no) as potential moderators by adding interactions with treatment arm to the primary outcome models.

Mechanisms: We will evaluate this using causal inference methods for mediation [95] using an instrumental variables approach (via two-stage least squares) to estimate the indirect effect of CBT_{BAR} on each of LIFE mania and LIFE depression scores via the HAPPI total score at the preceding time-point (e.g. 17-week HAPPI for 27-week LIFE scores). The more complex causal model incorporating BC and ISS will be investigated using structural equation modelling. As a post-randomisation effect modifier, the impact of the number of CBT_{BAR} sessions attended will be assessed using principal stratification methods; other measures of intervention receipt, including antidepressant medication, will be considered in separate analyses.

Secondary outcomes

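### The stated mediation power (88.5% / 83.5%) is that of a regression joint test, not of the two-stage least squares analysis that the protocol plans

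*Protocol*

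**What the plan says.** Protocol Section 3 (Sample size: quantitative work) makes this claim for the mechanism question: "286 participants with mediator and primary outcome data will also allow for 88.5% power for estimation of an indirect effect of 40" per cent, "or 83.5% power for the estimation of a 30% indirect effect". The inputs are given in the same sentence: "Assuming a standardised effect size of the intervention on the HAPPI of 0.4", and "based on a total effect on the intervention of the MCID (i.e. 0.5" points. The significance level is 2.5%. The software is the R package medssp, and the methods paper cited for it (reference 83 in Section 13) is, by its title, about sample size for jointly testing indirect effects.

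Protocol Section 8 (Co-primary outcomes, Mechanisms) then fixes how the indirect effect through HAPPI will be estimated: "using an instrumental variables approach (via two-stage least squares) to estimate the indirect effect of CBT_{BAR"} on each LIFE score. Structural equation modelling is kept for the larger model that adds BC and ISS. The protocol names no instruments, assumes no instrument strength and gives no power for 2SLS.

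**The concern.** The two sections describe different tests of the same quantity. A regression joint test asks whether the arm-to-HAPPI path and the HAPPI-to-LIFE path are both significant. The second path uses all the variation in HAPPI left after arm and covariates. 2SLS uses only the part of HAPPI that the instruments predict.

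Arm is a single instrument. It can identify one effect, so arm alone cannot separate an effect through HAPPI from an effect that bypasses it. Further instruments are needed, typically arm-by-baseline interactions. Precision then depends on how far the effect of CBT on HAPPI differs across those baseline characteristics, and Section 3 assumes nothing about this.

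Mechanism is one of the three research questions in Section 2 and has its own objective and hypotheses. An inconclusive 2SLS estimate read against a stated 88.5% power could be given more weight against HAPPI mediation than it deserves.

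**Working it through.** **Inputs (Section 3 unless stated).** n = 286. Effect on HAPPI 0.4 SD. Total effect 0.5 PSR points. Outcome SD 1.3 ("To detect a between-group mean difference of 0.5 points (SD=1.3 points [80"). Baseline correlation 0.4 ("assuming a conservative correlation of 0.4 between baseline and 27-week scores"), so residual SD = 1.3 × √(1 − 0.16) = 1.19. Allocation 1:1 (Section 12 counts 169 treated of 338). The 2.5% level is taken as two-sided, as Section 8 states for the co-primary tests (an assumption for mediation); critical value 2.241. The HAPPI-to-LIFE slope is b = share × 0.5/0.4, that is 0.50 (40%) or 0.375 (30%) points per SD of HAPPI.

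**Step 1: reproduce 88.5%.** Joint power = power(a-path) × power(b-path), normal approximation.
- a-path: 0.4 × 0.5 × √286 / SD(HAPPI given arm). If 0.4 is on the total SD, SD(HAPPI given arm) = √(1 − 0.4²/4) = 0.980, so 3.45 and power 88.7%. If it is on the within-arm SD, 3.38 and 87.3%.
- b-path, 40%: 0.50 × 0.980 × √286 / 1.3 = 6.37, power essentially 1.
- Product: 88.7% (or 87.3%), against 88.5% stated. A one-sided 2.5% test would give 92-93% and does not fit.

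**Step 2: the 30% figure.** b-path: 0.375 × 0.980 × √286 / 1.3 = 4.78, power 0.994; product 88.2%. Removing from the residual the variance explained by arm and HAPPI raises this to 88.5%. The documented inputs do not give 83.5%. With that same residual, both stated figures appear (88.55% and 83.53%) if 0.5/1.3 = 0.385 is entered as the total effect with SD 1.3. They also appear if 0.5 is entered with 1.69 in place of the SD. The two are equivalent, because 0.385/1.3 = 0.5/1.69.

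**Step 3: 2SLS with the documented inputs.** The b-path value is multiplied by √R2, where R2 is the share of HAPPI variance, beyond arm and covariates, that the instruments explain. Example, 40% effect at R2 = 0.05:
- Low end (within-arm scaling, outcome SD 1.3): 0.50 × √286 / 1.3 = 6.50; × 0.2236 = 1.45; power 0.216; × 0.873 = 18.8%.
- High end (total-SD scaling; residual variance net of baseline, arm and HAPPI = 1.69 × 0.84 − 0.50² × 0.96 − 0.5²/4 = 1.117, SD 1.057): 0.50 × 0.980 × √286 / 1.057 = 7.84; × 0.2236 = 1.75; power 0.313; × 0.887 = 27.7%.

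| Instrument R2 (assumed) | Joint power, 40% effect | Joint power, 30% effect |
|---|---|---|
| 0.005 | about 4% | about 3% |
| 0.05 | 19-28% | 11-15% |
| 0.10 | 37-53% | 21-29% |
| 0.20 | 65-80% | 42-54% |
| 0.30 | 79-87% | 57-71% |

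The choice of HAPPI scaling moves an entry by about one point at most. Simulated 2SLS with one or three arm-by-covariate instruments gave joint power, over both shares, of 1-15%, 12-36%, 27-54% and 50-76% at the first four strengths.

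**Step 4: what these R2 values mean.** With 1:1 allocation and HAPPI variance near 1, R2 is about τ²/4, where τ is the SD of the CBT effect on HAPPI across the instrument subgroups. So τ = 2√R2 = 0.14, 0.45, 0.63 and 0.89 for R2 = 0.005, 0.05, 0.10 and 0.20, against an assumed mean effect of 0.4. Covariates that reduce the HAPPI variance lower the τ needed.

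**The case against.** **Instruments and their strength are ordinary SAP content.** That is fair, and their absence from the protocol is not the complaint. The protocol itself states both the power and the estimator, without qualification, and the two do not match.

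**2SLS power could be respectable.** With strong instruments it could: at R2 of 0.20 to 0.30 the 40% case reaches about 65-87%. A reader might infer from weak-instrument scenarios that power is a few per cent to about 45%, and that a null result is the likely outcome. The documents do not support a fixed range, because they give neither instruments nor strength. If arm were the only instrument, the test would be close to the total-effect test, with about 90% power. But it would force the direct effect to zero, which contradicts an indirect share of 30% or 40%.

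**The instruments look invalid.** Section 8 says "We will explore BAR group (I, II or II) and prior CBT (yes; no) as potential moderators". A reader might infer that using arm-by-BAR-group or arm-by-prior-CBT as instruments breaks the exclusion restriction. It does not follow. The moderator analysis concerns the total effect, while the restriction concerns the direct effect. If CBT changes HAPPI more in some groups and HAPPI drives LIFE, moderation of the total effect is expected.

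**The MCID was standardised twice.** This might be inferred from Step 2, but another entry gives the same pair of figures, and the inputs used are not shown.

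**Conclusion.** The point holds: 88.5% / 83.5% is not the power of the planned 2SLS analysis, and it overstates that power at every instrument strength tried (R2 up to 0.30). The size of the gap is conditional on R2, which is an assumption here and not a document figure. The calculation also rests on a two-sided 2.5% level for mediation, the normal approximation, and success defined as both paths being significant.

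The mismatch for the 30% figure (about 88% from the documented inputs, 83.5% stated) is minor. It errs on the cautious side for the regression test, and its cause cannot be settled from the text.

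The sample size of 338 is set by the co-primary ANCOVA and does not change. The point should be fixed, but it does not threaten the primary analysis.

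**What to change.** In Section 3, do one of the following:

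- Replace the two figures with simulated 2SLS power at 286, under named instruments and over a stated range of instrument strength; or
- State that 88.5% / 83.5% applies only to a regression-based joint test, and report that test alongside 2SLS in Section 8 with its assumption of no unmeasured mediator-outcome confounding.

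Which estimator leads is a judgement for the trial team: regression is more precise but needs that assumption, while 2SLS relaxes it at a cost in precision. Where the joint-test figures are kept, check the inputs and recompute with total effect 0.5 and SD 1.3.

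The cost is wording in one or two sections, plus one simulation under the first option or a recomputation under the second. The downside is a less favourable mediation power statement for 2SLS.

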4. PARTICIPANT ELIGIBLITY CRITERIA

MAIN TRIAL

Inclusion criteria

The study population are young people meeting BAR criteria. The inclusion criteria are:

- 16-25 years old
- Meet criteria for one of the following:
 - Group I: Sub-threshold mania:
 - For at least 2 consecutive days but less than 7 days: period of abnormally and persistently elevated, expansive or irritable mood + at least 2 criteria from the list (≥ 3 for irritable mood):
 - (1) inflated self-esteem/grandiosity, (2) decreased need for sleep, (3) more talkative than usual, (4) flight of ideas/racing thoughts, (5) distractibility, (6) increase goal directed activity or psychomotor agitation, (7) excessive involvement in activities that have a high potential for painful consequences.
 - **Group II**: Depression + Cyclothymic features:
 - i. Depression (for at least 1 week): depressed mood / loss of interest or please + 2 criteria from the list:
 - (1) significant weight loss, (2) insomnia or hypermania nearly every day, (3) psychomotor retardation/agitation, (4) fatigue/loss of energy, (5) feelings of worthlessness/excessive or inappropriate guilt, (6) diminished ability to think or concentrate, (7) recurrent thoughts of death/suicidal ideation

PLUS

- ii. Cyclothymic features: numerous episodes with sub-threshold manic symptoms not meeting Group 1 criteria: subthreshold mania as defined in Group 1 for 4 hours within 24-hour period and at least 4 cumulative lifetime days in the past 12 months.
- **Group III**: Depression + genetic risk:
 - i. Depression (See Group 2)
 - PLUS
 - ii. Genetic risk: first degree relative with BD
- Help seeking
- Provision of written informed consent

Exclusion Criteria

- History of a treated/untreated manic episode or psychosis of 1-week duration or longer
- Treatment with a mood stabiliser for longer than 6-weeks or antipsychotic for 3-weeks [evidencing exclusion on point above or at the time of the assessment whereby at-risk status cannot be confirmed]
- Organic brain disorder
- Unable to complete assessments due to language barriers
- Inpatient/acute psychiatric care needed
- Primary substance abuse / dependency

NESTED QUALITATIVE STUDIES

All participants will be eligible to take part in the nested qualitative study. This also applies to their family / carers who they might refer to be invited to take part in the nested qualitative study. In addition, stakeholders

who come in to contact with young people that meet BAR criteria will also be considered as suitable for the nested qualitative interview. This could include university counselling staff, primary care psychology therapists, and psychiatrists working in the NHS.

5. TRIAL PROCEDURES

RECRUITMENT & PARTICIPANT IDENTIFICATION

We plan to use study settings and an approach to recruitment which has been highly successful in our previous trials involving the detection and intervention for people at high risk of developing more serious/long-term mental health problems e.g. psychosis (MRC funded EDIE-II trial); complex long-term mental health problems (HTA funded PRODIGY trial); bipolar disorder (BART RfPB pilot study). These previous trial experiences have provided valuable lessons regarding how to facilitate referral pathways into the BART II trial.

The approaches used previously have consisted of utilising outreach principles where participants are seen in non-stigmatising settings. This means that people often choose to be seen at home. However, other least restrictive venues e.g. youth centres, colleges, primary care settings, are also employed. Additionally, the trial will be conducted within the infrastructure of the research network as this is designed and resourced to support recruitment to large-scale studies.

To ensure the study results are readily translatable for patients within the current NHS, recruitment will involve casting our net into a variety of established services including children and young people's mental health services (CYPMHS), early intervention (EI) and detection (EDIT), community mental health teams (CMHT), increasing access to psychological treatments services (IAPT), primary care psychology services and GPs.

Recruitment will also include school/university health services and other youth services and the voluntary sector. This approach will both enhance generalisability and feasibility, given our experiences from the early detection trials and services and the pilot work which underpins this research. The aforementioned recruitment strategy fits with the research of the pathways to care often experienced by people presenting with concerns about mood swings or familial risk of bipolar disorder. Throughout the lifetime of the trial, we will document all enquiries, referrals and randomisations from each team in order to capture potential sources of bias.

Materials for advertising the study will include participant leaflets, referrer leaflets, posters, participant information sheets, and animation videos. The participant leaflets and posters were designed with our PPI group from our RfPB trial which outlines information considered to be relevant to the population in order to make decisions about whether or not to take part in the research. The animation videos will depict participation in the trial including expectations and potential risk and benefits derived from service user participant work from our RfPB trial and our newly organised SURG for this trial. In addition, we will be advertising the study on the lead site research department website and through our social media channels (BART twitter account and lead site research department instagram account). The leaflets and posters will be replicated from the RfPB study materials as these were designed at the time with a BAR Service User Reference Group and a creative designer who supported in the presentation of the information. The animation will be developed prior to the start of this trial, with the support of the newly developed SURG groups. The animations will include a specific animation for potential participants, to explain the process of taking part in the study (who the study is for, the random allocation process and what the study will involve at each time point).

Participants will be identified by a professional who is involved in their care or is known to them as being potentially eligible for the trial or will be able to self-identify. In addition to the study being advertised on social media and through the lead site research department website and similarly through other Trust sites, leaflets and posters will be displayed in settings such as waiting rooms for NHS services. The research team will be making contact and developing links with a range of mental health professionals and services (both in the

community and in the NHS setting). Developing these links will include the research team being available for brief presentations of the study, regular contact (both face to face and via electronic or telephone means) and providing training opportunities around better understanding the BAR population and what the CBT_{BAR} trial entails.

The leaflets and posters will have the contact details for who to contact in the research team when making a referral. When a referral is made, the member of the research team will conduct a brief screening check and check verbal consent to contact. Full details about the process for accepting referrals, making initial contact with a referred participant, and conducting the baseline assessment are explained in more detail in the Research Assistant Manual.

Eligibility will be confirmed with the assessor who conducted the baseline assessment and with a member of the research team based at the central site (Manchester) or with the local site lead or PI. The outcome will be recorded on an eligibility review form entered on REDCap (Research Electronic Data Capture).

CONSENT

Verbal consent to contact will be sought by a relevant professional involved in the potential participant's care (e.g. GP, university counsellor). To aid this initial discussion, all potential participants will be provided with access to the study materials described above (leaflet, animation, etc). Prior to taking written, informed consent, all potential participants will be provided with a Participant Information Sheet. This will be either given in person to the potential participant by the relevant professional involved in their care, e-mailed, or sent to them in the post. Participants will be in receipt of the PIS for at least 24 hours prior to providing written, informed consent.

Written, informed consent will be taken in person at a face-to-face appointment with the research assistant. However, in the event there are restrictions in place that prevent a face-to-face appointment (e.g. COVID-19 related restrictions) we will utilise existing approaches to taking consent remotely (approved by the sponsor including audio recording the consent appointment) and obtaining written consent when it is possible to meet face-to-face. Audio recording will be done in line with the sites NHS policy and procedures. Audio recording of consent will follow the sites local NHS Trust policies and procedures. Audio recordings will be transferred to a secure NHS drive and will only be accessible by members of the research team with delegated responsibility to access, as per the study delegation log.

**Please refer to the BART II Participant Flow Diagram found in Appendices (#1)

PAYMENT

Participants will receive a £20 payment upon completion of the baseline and each follow-up appointment at 17-, 27-, and 52-weeks (£80 in total). In addition, a 39-week check in phone call will be conducted with each participant to confirm that contact details remain the same.

THE RANDOMISATION SCHEME

Eligibility will be confirmed via completion of the eligibility review form following the baseline assessment. This will be completed at an eligibility supervision between the research assistant and a supervisor (central site supervisor e.g. CI or trial manager, or local site lead or PI with delegated responsibility). The outcome of the eligibility review form will then need to be entered onto REDCap within 2 working days of completion of the review. If the person is eligible, randomisation will be undertaken automatically once entered in REDCap. Participants will be randomised to one of two trial arms (CBT_{BAR} + TAU **or** TAU alone). Randomisation will be independent and concealed, using permuted stratified blocks (using site and BAR Group*), via a web-based system at York Clinical Trials Unit.

*Confirmed BAR Group will be based on hierarchical rule system. Group 1 will be the stratification grouping for any participants meeting Group 1 and another BAR group (e.g. meets criteria for BAR Group 1 and 2). Group 2 will be the stratification grouping for any participants that meet BAR Group 2 and 3).

METHOD OF IMPLEMENTING THE RANDOMISATION/ALLOCATION SEQUENCE

The allocation is made known to the trial manager (to monitor adherence to the randomisation algorithm), the local trial administrator, local PI or site lead, and local trial therapist(s) by email and SMS text message. The allocation is made known to the participant by letter from the local trial administrator. Blinding of the allocation code will be maintained for research assistants.

BLINDING

Single blind – assessors will be blind to treatment condition. Blindness will be maintained using a wide range of measures which we have implemented successfully in other single blind trials within our trust research departments. These include separate offices for the therapists and research assistants, protocols for answering telephones including reminders for clinicians, participants and family members about the blind, protocols for message taking and secretarial support, separate diaries and pigeon holes and data file security, using passwords and encryption of randomisation information.

We will develop a standard operating procedure (SOP) for maintaining, recording, and managing blinding, which will outline all of these procedures. This SOP will be reviewed by, and agreed with, our DMEC and TSC. Each researcher will sign this SOP to confirm they understand and will comply with the blinding procedures. All blind breaks will be recorded by the trial manager and reviewed by the Chief Investigator for patterns in unblindings and be reported to the TSC and DMEC. There is only one follow-up scheduled during the intervention window (at 17-weeks). This will reduce the risk of blind breaks occurring because of therapists and RAs crossing paths for visits and it will reduce the opportunity for unblinding to occur because of communication with participants to arrange visits. Our qualitative researcher WJ will be conducting interviews with participants who have received the CBT_{BAR} intervention, and this poses an unblinding risk if the RAs learn which participants met with WJ. All interviews for the qualitative research by WJ with the participants will occur at a timepoint away from a standard follow-up point and will be overseen by the trial manager to ensure participants and the RA's are not in contact.

Maintaining rater blindness to treatment allocation is crucial. Following eligibility assessment and completion of baseline assessments, participants will be allocated to treatment groups through our web-based randomisation service and the Trial administrator will inform the participants of this decision. All letters to participants and clinicians will contain a standardised statement about the need to maintain the single blinding process. Any accidental unblindings will be recorded. Where possible, we will identify an independent assessor with whom the blinding has not been broken to complete subsequent follow-ups, subject to any threats to participant engagement with follow-up.

TRIAL ASSESSMENTS

Following the recruitment process, baseline assessment and randomisation, follow-up assessment points will be at 17-, 27-, and 52-weeks post-randomisation (see "Schedule of Events" in the Appendices (#2)). We will also contact people via telephone at 39-weeks to promote retention in the trial and ask about general wellbeing since the last assessment (including documenting any potential serious adverse events, and any changes to contact details). Assessments will be conducted by research assistants blind and independent to treatment group and will employ both a semi-structured interview to gather data for the primary outcome (blinded) and secondary outcomes in addition to self-report questionnaires (unblinded data given the participant will be aware of their treatment allocation). The self-report questionnaires will be offered for completion in paper format.

For those participants who are offered the CBT_{BAR} intervention, a measure of therapeutic alliance (California Psychotherapy Alliance Scales / CALPAS) will be administered to both the participant and the therapist for completion after the 4th and 10th sessions. To ensure the participant is able to complete the measure openly, the trial manager (LP) will be responsible for contacting the participant and arranging administration of this measure to prevent the therapist being the person to do this. Additionally, the Facilitative Alliance Measure will be administered by the trial manager (LP) to the research participants following each follow-up appointment with a research assistant. This will measure alliance with the research assistant.

Follow-up visits are typically offered via face-to-face methods utilising outreach principles where participants are seen in non-stigmatising settings. This approach means that people often choose to be seen at home although other least restrictive venues e.g. youth centres, colleges, primary care settings, are also employed. Staff training will be conducted with all staff and regular arrangements for ensuring inter-reliability across sites. Adapting to assessments via phone/virtual calls still retains validity and reliability on our primary outcome [84].

QUALITATIVE RESEARCH

Nested qualitative research will examine the perceived mechanisms of change and implementation for NHS patients. After the 26-week treatment window participants will be offered the opportunity to take part in the nested qualitative study. Semi-structured interviews will explore participants' experiences of receiving CBT_{BAR} and ways in which service users perceive the mechanisms by which CBT_{BAR} causes improvements in depression and mania symptoms including key psychological processes targeted with this treatment (e.g., extreme appraisals of mood states, behaviours employed to provide coping). Additionally, interviews will seek to understand themes associated with the implementation of CBT_{BAR}.

Mechanistic objective

To determine ways in which service users perceive the mechanisms by which CBT_{BAR} causes improvements in depression and mania symptoms including key psychological processes targeted with this treatment (e.g., extreme appraisals of mood states, behaviours employed to provide coping). We will we undertake a nested qualitative study seeking to understand how participants experience or perceive the intervention to have impacted on their mood, behaviours and symptoms and draw patterns across participants' experiences. We will seek to identify components of the intervention that participants continued to utilise beyond therapy, and ways they have incorporated these into their lives. Achieving this mechanistic objective has the potential to refine and adapt the treatment model being tested within the trial.

Implementation objective:

In order to identify key themes associated with the implementation of CBT_{BAR} in NHS services we will undertake a nested qualitative study to identify potential barriers and solutions to future implementation. Key stakeholders will include service users randomised to treatment, family members, health professionals', service providers' within areas of likely service contact for the potential user (e.g. IAPT, CYPMHS, Early Intervention or At Risk Mental State teams) and commissioners. This will provide vital information to maximise the likelihood that our intervention can be delivered efficiently and effectively within the NHS after the trial has finished.

WITHDRAWAL CRITERIA

A participant is free to withdraw from the trial at any point if they wish to do so, without giving a reason and without it affecting their care. If a patient withdraws consent to participate, clarification will be sought on whether withdrawal is from the intervention component (CBT_{BAR}), and/or completing the assessments (clarifying if this includes both or either the semi-structured interviews and the self-report measures). A participant who chooses to withdraw from an intervention arm will be encouraged to continue with research assessments if they are happy to do so.

Withdrawal can also include the clinical decision by the trial therapist at site to cease or alter trial treatment, and potentially withdraw the patient from treatment. Examples of why this might be completed could include loss of capacity to consent or significant change to the person's circumstances such as significant issues with drugs or alcohol. This would be classed as "Treatment Discontinuation" on the withdrawal form. Clarification would be needed by the clinician if the research team should continue to contact the participant as normal at the follow-up points.

For those participants who take part in the nested qualitative study, they will be free to withdraw from this as well. The qualitative study will be a one-off qualitative interview; however, it could be the person initially agrees to take part but does not finish the interview. Or the person later seeks to withdraw their interview from use in the analysis.

Data collected up to the date of withdrawal of consent will be used in the analyses unless the person requests the data is not used. If necessary or helpful, an unblinded member of the research team (e.g. trial manager) will aim to have a discussion with the participant regarding their wishes.

The information about the withdrawal will be captured on a withdrawal form at site and entered onto REDCap.

